5.3.2 Index Test

The Xpert MTB/XDR assay detects Mtb mutations associated with INH, ETH and second-line drug resistance direct from sputum. In line with this intended use, clinical samples will be directly tested by the Xpert MTB/XDR assay. However, the assay will also be used to test the culture isolate. This additional Xpert MTB/XDR assay testing will allow for a comparison of performance and non-determinant rates between testing directly from the sample and testing from the culture isolate. It will also support resolution of potential discordant LPA and NGS results from the initial Xpert MTB/XDR test result, as these tests will also be performed from the culture isolate (discordance may arise as a result of infections with a mix of different strains, with only one strain being grown out in culture). Furthermore, as all assays will be performed on the same culture, there is also no risk of any assay being tested on a different quality sample.

Review bias will be avoided in this study as the index test requires no manual interpretation by the operator. All results are automatically generated by the GeneXpert instrument and will be directly recorded by the operator on the laboratory case report form (CRF).

5.3.3 Reference Standard and Comparators

There is little risk of reference standard bias in this study as a composite reference standard of phenotypic DST and NGS will be used for resistance detection (Table 1). The use of both phenotypic and genotypic information will ensure high confidence in the reference standard, as certain mutations (e.g. many *eis* promoter mutations) are known to confer only low-levels of phenotypic drug resistance, and so they may not be detected by phenotypic DST at only one critical concentration. Furthermore, all molecular assays evaluated in this study detect resistance-mutations in similar gene regions, and so all mutations that are detectable by the Xpert MTB/XDR assay are generally detected by NGS and/or the Hain LPAs and vice versa.

Table 1. Composite reference standard for diagnostic performance analysis

Composite Reference Standard		
Drug of Interest	NGS of Reference Gene(s)	MGIT960 Phenotypic DST
Isoniazid	katG , fabG1 , inhA promoter, ahpC promoter	Isoniazid
Ethionamide	inhA promoter	Ethionamide

Fluoroquinolones		
Moxifloxacin	gyrA, gyrB	Moxifloxacin
Levofloxacin	gyrA, gyrB	Levofloxacin
Second-line Injectables		
Amikacin	rrs	Amikacin
Kanamycin	rrs, eis promoter	Kanamycin
Capreomycin	rrs	Capreomycin

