7.1 Reference Standard Test and Index Test Procedures

A composite reference standard of phenotypic DST and NGS will be used for resistance detection to ensure high confidence in the reference standard for this study. Phenotypic MGIT DST and targeted NGS will be performed on the culture isolate for each clinical sample. MGIT DST will be done on site to determine culture drug-susceptibility to INH, ETH, moxifloxacin, levofloxacin, AMK, KAN and CAP at the revised WHO critical concentrations¹⁵. Targeted NGS of the gene regions included in the Xpert MTB/XDR assay will be performed on DNA extracted from the cultured sample, which will be sent to a SNRL for NGS, or sequenced locally using primers specific for the gene regions included in the assay. The output for both phenotypic DST and NGS results are automated, and require no manual operator interpretation. Testing results, when obtained, will be input onto the laboratory CRF.

The index test will be performed on both the direct clinical sample as well as the culture isolate, to ensure high Xpert MTB/XDR diagnostic performance direct from sputum and to provide a basis for comparison if any discordants are seen between the initial Xpert MTB/XDR result and the phenotypic DST and additional molecular test results (NGS and LPA). The output for the Xpert MTB/XDR assay is automated and does not require manual interpretation. As with the reference test, all Xpert test results will be noted on the laboratory CRF.

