9.2.2 Definitions for Diagnostic Performance Analysis

TEST RESULT	DESCRIPTION
Phenotypic Drug*-resistant	Culture-positive and growth for Drug* in conventional DST testing.
Phenotypic Drug*-sensitive	Culture-positive and no growth for Drug* in conventional DST testing
Genotypic Drug*-resistant	NGS identifies mutations recognized to be associated with resistance (defined based on consultation with WHO prior to analysis)
Genotypic Drug*-sensitive	NGS identifies no mutations recognized to be associated with resistance (defined based on consultation with WHO prior to analysis)
Composite reference standard Drug*-resistant	If Phenotypic Drug*-sensitive but NGS identifies mutations recognized to be associated with Drug* resistance for the respective gene regions, the composite reference standard will be considered Drug*-resistant. If Phenotypic Drug*-resistant but NGS does not identify mutations recognized to be associated with Drug* resistance for the respective gene regions, the composite reference standard will be considered Drug*-resistant (as mutations will be assumed outside of the region sequenced).

Composite reference standard Drug*-sensitive | If Phenotypic Drug*-sensitive and NGS shows either no mutations or only mutations that are not associated with Drug* resistance for the respective gene regions.

* Drug: INH, ETH, FQ (moxifloxacin and levofloxacin for phenotypic DST), AMK, KAN or CAP

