The results will serve as an early indicator of Xpert MTB/XDR accuracy in the clinical trial. If performance estimates fall outside of the presented confidence intervals for resistance detection (Table 2), the Data Monitoring Committee (DMC) will review all data for accuracy and consistency. Additionally, the sponsor may conduct a monitoring visit to one or more sites to ensure adherence to SOPs and effective data management.

7 Additional sub-group analyses

Subgroups analyses, and definitions of subgroups, are described in section 4.3. No additional subgroup analyses will be performed.

8 Multiple comparisons/multiplicity adjustments

No multiple testing of statistical hypotheses is going to be performed.

9 Exploratory analyses

No exploratory analyses will be performed.

10 Sample size

To achieve the targeted precision for accuracy estimates, it is estimated that 760 samples will need to be tested for this study, with a final 284 MTB-positive and an additional 316 RIF-resistant samples tested by Xpert MTB/XDR and all reference standards and comparators, i.e. a total of 600 specimen results available for analysis. The desired precision for the accuracy estimates was chosen to achieve high confidence in the estimates for Xpert MTB/XDR resistance detection when considering evidence from both the 'external laboratory validation' (phase I) and the clinical trial (phase II). The sample size is detailed below in Table 2.

		n	Point estimate (95%CI) *	Total width of CI *
INH	Sensitivity	395	90% (86, 93)	7%
	Specificity	205	98% (95, 99)	4%
FQs	Sensitivity	93	90% (82, 95)	13%
	Specificity	507	98% (96, 99)	3%
AMK	Sensitivity	34	90% (74, 97)	23%
	Specificity	566	98% (96, 99)	3%
KAN	Sensitivity	71	90% (80, 96)	16%
	Specificity	529	98% (96, 99)	3%
CAP	Sensitivity	34	90% (74, 97)	23%
	Specificity	566	98% (96, 99)	3%

Table 2 Sample size

* 95%CI based on Wilson's score method (as recommended by Newcombe et al. as well as CLSI/FDA) using continuity correction.

11 Minimization of error and bias

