11.1 Enrolment and randomization procedures

Describe how enrolment will be carried out (from the clinical protocol) and add details on the randomization procedure (if applicable)

12 Case definitions

Table 3 describes the categorization of results based on test results.

TEST RESULT	DESCRIPTION
Phenotypic Drug*-resistant	Culture-positive and growth for Drug* in conventional DST testing.
Phenotypic Drug*-sensitive	Culture-positive and no growth for Drug* in conventional DST testing
Genotypic Drug*-resistant	NGS identifies mutations recognized to be associated with resistance (defined based on consultation with WHO prior to analysis)
Genotypic Drug*-sensitive	NGS identifies no mutations recognized to be associated with resistance (defined based on consultation with WHO prior to analysis)
Composite reference standard Drug*-resistant	If Phenotypic Drug*-sensitive but NGS identifies mutations recognized to be associated with Drug* resistance for the respective gene regions, the composite reference standard will be considered Drug*-resistant. If Phenotypic Drug*-resistant but NGS does not identify mutations recognized to be associated with Drug* resistance for the respective gene regions, the composite reference standard will be considered Drug*-resistant (as mutations will be assumed outside of the region sequenced).
Composite reference standard Drug*-sensitive	If Phenotypic Drug*-sensitive and NGS shows either no mutations or only mutations that are not associated with Drug* resistance for the respective gene regions.

* Drug: INH, ETH, FQ (moxifloxacin and levofloxacin for phenotypic DST), AMK, KAN or CAP

Table 3 Case definitions

13 Statistical software

The analysis will be performed using the R statistical language (version 3.4.0 or higher) on OsX, and Microsoft Excel 2018 (version 16.16 or higher).

14 References

Add required references.

15 Document history

Version	Notes / Changes
1.0	Initial version

16 Appendix

The definitions of composite reference standards are given in table 4.

DRUG RESISTANCE	COMPOSITE REFERENCE STANDARD
INH-resistant	NGS of katG , fabG1 , ahpC and inhA detects ≥ 1 mutation associated with INH resistance and MGIT culture is INH drug-resistant at the critical concentration.
ETH-resistant	NGS of inhA detects ≥ 1 mutation associated with ETH resistance and MGIT culture is ETH drug-resistant at the critical concentration.

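### The sequencing half of the composite reads the same gene regions as Xpert MTB/XDR and keeps DST-susceptible/NGS-mutant samples out of the specificity denominator; no final analysis reports accuracy against phenotypic DST alone

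*Protocol*

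**What the plan says.** Protocol section 5.3.3 opens its case for the reference standard with "There is little risk of reference standard bias in this study as a composite reference standard of phenotypic DST and NGS will be used". The same paragraph says that the molecular assays look at similar regions, "so all mutations that are detectable by the Xpert MTB/XDR assay are generally detected by NGS and/or the Hain LPAs and vice versa". Section 7.1 is explicit about the overlap: "Targeted NGS of the gene regions included in the Xpert MTB/XDR assay will be performed on DNA extracted from the cultured sample".

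The documents hold two different composite rules.

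- Protocol section 9.2.2, repeated in SAP section 12 (Table 3), is an either-positive rule. The composite is resistant in the case "If Phenotypic Drug*-sensitive but NGS identifies mutations recognized to be associated with Drug* resistance for the respective gene regions", and also in the case "If Phenotypic Drug*-resistant but NGS does not identify mutations recognized to be associated with Drug* resistance for the respective gene regions".
- SAP Appendix (section 16), Table 4, requires agreement. For INH, a resistant sample needs a "mutation associated with INH resistance and MGIT culture is INH drug-resistant at the critical concentration"; a susceptible sample needs both components negative. The other drugs follow the same pattern.

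SAP section 4.2 refers to the Appendix for outcomes 1.1 to 1.3 and uses only the composite, on the per-protocol set. The interim analysis (protocol section 9.3, SAP section 6) uses NGS alone. In the final analysis, the only item tied to NGS is the per-gene detection count in SAP section 4.3. SAP section 9 adds "No exploratory analyses will be performed". No section plans sensitivity and specificity against phenotypic DST alone.

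**The concern.** Phenotypic DST is the only part of the reference that does not depend on the index test's own targets. Suppose an isolate is DST-susceptible but has a listed mutation, and Xpert finds that mutation. Against DST this is a false positive. Under either composite rule it cannot be one: the sample is counted as a true positive or is left out. A composite false positive then requires Xpert to disagree with sequencing of the same regions, or to call a mutation that is not on the list. Protocol section 9.2 tightens the link, because the isolate's Xpert result is used when sputum and isolate disagree, and the isolate is the material that is sequenced.

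The protocol expects some samples of this kind: section 5.3.3 names many *eis* promoter mutations as low-level and liable to be missed by DST. As planned, the final report would not show how often Xpert calls resistance in phenotypically susceptible TB, and readers could not judge how much of the reported specificity depends on the choice of reference.

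**Working it through.** **1. The plan's own figures.** Table 2 uses the Wilson score interval with continuity correction. With q = 1 − p and z = 1.96:

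- lower = {2np + z² − 1 − z√[z² − 2 − 1/n + 4p(nq + 1)]} / {2(n + z²)}
- upper = {2np + z² + 1 + z√[z² + 2 − 1/n + 4p(nq − 1)]} / {2(n + z²)}

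At p = 0.98, n = 205 (INH) gives 94.7 to 99.3, stated as 95 to 99. At n = 529 (KAN) it gives 96.3 to 99.0, stated as 96 to 99. The counts also reproduce from Appendix 4: INH-resistant 82 + 313 = 395; KAN-resistant 3 + 68 = 71.

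**2. The four result patterns under each rule.**

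| DST | NGS mutation | Protocol 9.2.2 / SAP Table 3 | SAP Table 4 | DST alone |
|---|---|---|---|---|
| Resistant | Yes | Resistant | Resistant | Resistant |
| Susceptible | Yes | Resistant | No class | Susceptible |
| Resistant | No | Resistant | No class | Resistant |
| Susceptible | No | Susceptible | Susceptible | Susceptible |

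The specificity denominator is the last row under both composite rules. Only DST alone adds the second row.

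**3. Formula.** Let S be the composite-susceptible count, Sp the composite specificity, g the number of DST-susceptible/NGS-mutant samples, and d the proportion of these that Xpert calls resistant.

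- DST-alone specificity = [Sp × S + (1 − d) × g] / (S + g)
- Composite minus DST-alone = g × [d − (1 − Sp)] / (S + g)

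The difference is positive when g > 0 and d exceeds 1 − Sp, here 2%. It is zero when g = 0.

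**4. Numbers.** S and Sp = 0.98 are from Table 2. Both g and d = 0.98 are assumptions.

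| Drug | S | g | Calculation | DST-alone specificity |
|---|---|---|---|---|
| INH | 205 | 5 | 201.0/210 | 95.7% |
| INH | 205 | 10 | 201.1/215 | 93.5% |
| INH | 205 | 20 | 201.3/225 | 89.5% |
| FQ | 507 | 9 | 497.04/516 | 96.3% |
| KAN | 529 | 7 | 518.56/536 | 96.7% |
| KAN | 529 | 14 | 518.70/543 | 95.5% |
| KAN | 529 | 21 | 518.84/550 | 94.3% |

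Lowering d to 0.90 changes little: INH at g = 10 gives 201.9/215 = 93.9%, and KAN at g = 14 gives 519.82/543 = 95.7%.

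The g values above are different shares of the resistant group (10/395 = 2.5% for INH; 14/71 = 20% for KAN). With the same assumed share for every drug and d = 0.90:

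| Share of composite-resistant | INH | FQ | KAN | AMK or CAP |
|---|---|---|---|---|
| 0% | 98.0% | 98.0% | 98.0% | 98.0% |
| 5% | 90.3% | 97.2% | 97.4% | 97.7% |
| 10% | 83.8% | 96.4% | 96.8% | 97.5% |
| 20% | 73.5% | 94.9% | 95.7% | 97.0% |
| 30% | 65.8% | 93.4% | 94.6% | 96.4% |

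INH is the most exposed arithmetically because only 205 samples are composite-susceptible against 395 resistant. ETH has no row in Table 2, so no figure can be given.

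**5. Sensitivity.** Moving g samples barely affects it: for INH with g = 10, (0.90 × 395 − 0.98 × 10)/(395 − 10) = 345.7/385 = 89.8%, against 90%. The choice of composite rule matters more. Assume 95% detection when a mutation is present, 2% when absent, and 5% of resistant samples DST-resistant/NGS-negative. The either-positive rule gives 0.95 × 0.95 + 0.05 × 0.02 = 90.35%. Table 4 drops the last group and gives 95.0%.

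**The case against.** Including NGS is a reasoned choice. Section 5.3.3 argues that DST at a single critical concentration can miss low-level resistance. If the listed mutations mark true resistance, the composite is nearer the truth and DST-alone specificity would be too low. The mutation list comes from consultation with WHO, not from the cartridge, so an Xpert call on a mutation not associated with resistance remains a false positive. The either-positive rule also works against the assay, because DST-resistant samples without a mutation count as resistant. The per-gene count in SAP section 4.3 shows misses when a mutation is present, which goes part of the way to separating assay error from mechanisms that the assay does not target. All of this stands.

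Four stronger readings are tempting and are not supported:

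- That primary specificity is inflated by construction. This is shown only relative to phenotypic DST, which the protocol treats as imperfect.
- That the SAP primary analysis overrides a susceptible DST. Table 4, the definition that section 4.2 cites, leaves such samples without a class.
- That NGS alone is used only at the interim analysis. The final per-gene count uses it too, although it gives no sensitivity or specificity.
- That discordance is expected for every drug. The only low-level example named is *eis*, which the protocol's background section ties to KAN alone. The large INH figures show arithmetic exposure, not a forecast.

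Comparing DST-alone values with the Table 2 intervals would also mix two estimands, since those intervals describe planned precision for the composite. And SAP section 7 limits subgroups, which a change of reference is not; section 9 is what closes off further analyses.

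None of this supplies the missing result. Table 4 shields specificity by omission where section 9.2.2 does so by reclassification. Table 4 also removes the DST-resistant/NGS-negative samples, and with them the phenotypic check on sensitivity.

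**Conclusion.** The point holds as a gap in reporting and as an unsupported assurance in section 5.3.3. Under either composite rule, DST-susceptible/NGS-mutant samples are outside the specificity denominator, so composite specificity is at or above DST-alone specificity provided that Xpert calls those samples resistant more often than it calls composite-susceptible samples resistant. Whether the difference is bias against true resistance cannot be settled from the documents.

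Its size depends on a discordance rate that the documents do not give. At the planned 98% composite specificity and an assumed 98% detection, 10 discordant INH samples correspond to a gap of about 4.5 points (98.0 to 93.5%), and 14 discordant KAN samples to about 2.5 points (98.0 to 95.5%). The gap is zero without discordance. The conflict between the two composite rules is certain from the text, and it decides whether sensitivity faces a phenotypic check. This is worth correcting because it changes what the trial can report and uses data already planned.

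**What to change.** 1. Reconcile protocol section 9.2.2 and SAP Table 3 with SAP Appendix Table 4. Adopt one composite definition, state how each of the four DST/NGS patterns is classed, and keep it as the primary reference.
2. In SAP section 4.2, pre-specify supplementary analyses for each drug in outcomes 1.1 to 1.3: sensitivity and specificity with Wilson intervals against phenotypic DST alone and against NGS alone, and the NGS-by-DST 2×2 with the Xpert result in each cell. Run them on the same per-protocol samples, including any that the composite leaves unclassified, so that differences reflect the reference and not the sample set.
3. Replace the opening sentence of protocol section 5.3.3 with a statement that the NGS component shares the index test's targets and can favour its specificity relative to phenotypic DST.

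The cost is a change of wording and a few more result tables. DST and NGS are already scheduled on the isolates, and section 9.2.2 already defines the phenotypic and genotypic classes separately. These are estimates without hypothesis tests, so no multiplicity issue arises. The downside is that a less favourable specificity may go on record.

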5.3.4 Laboratory Methods

The participating sites will undergo an on-site laboratory and clinical evaluation during the site initiation visit to ensure standardized and high-quality performance of molecular methods.

6 Study Procedures

Study procedures and their timing are summarized in the Schedule of Assessments. Protocol waivers or exemptions are not allowed.

Adherence to the study design requirements, including those specified in the Schedule of Assessments, is essential and required for study conduct.

All screening evaluations must be completed and reviewed to confirm that potential participants meet all eligibility criteria. The investigator will maintain a screening log to record details of all participants screened and to confirm eligibility or record reasons for screening failure, as applicable.

Procedures conducted as part of the participant's routine clinical management (e.g., blood count) and obtained before signing of the ICF may be utilized for screening or baseline purposes provided the procedures met the protocol-specified criteria and were performed within the time frame defined in the Schedule of Assessments.

6.1.1 Sample Selection

Up to two sputum samples ($\geq 3\text{mL}$) will be collected from consecutive, prospectively-enrolled patients with defined risk factors for DR-TB and a valid Xpert MTB/RIF or Xpert MTB/RIF Ultra result. Depending upon enrolment rates, study timelines may be accelerated by also using existing, well-characterized frozen TB clinical (sputum) samples collected during the course of routine clinical care and TB surveillance in the sites of intended use. These samples will only be used if recruitment or enrolment is slow at one or more sites. At the 4-week study time point, recruitment rates will be assessed to determine whether this use of additional samples will be necessary.

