5.3 Minimization of Error and Bias

5.3.1 Patient Selection

A consecutive series of Xpert MTB/RIF MTB-positive patients (n=284) will be enrolled in this study, followed by an additional, consecutive series of Xpert MTB/RIF RIF-resistant patients (n=316) between the three countries with participating clinical sites. Enrolment will be based upon clearly defined eligibility criteria.

Analyses will be conducted for relevant sub-groups of the enrolled TB patient population (i.e. smear status for TB, drug-resistance profile, mutations detected, etc.), which may be considered to be indicators of disease severity.

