All diagnostic test results (smear, Xpert MTB/XDR on direct sample, MGIT, LJ, Xpert MTB/XDR on culture isolate, MTBDR*plus*, MTBDR*sl*, DST and NGS results) will be recorded by the laboratory technicians for each site on the laboratory CRF.

7 Specimen Collection, Handling, Transport and Storage

Clinical (sputum) samples from enrolled patients will be used in this study. Patients will be asked to provide up to two sputum samples for testing after providing informed consent for the study. Sputum samples from the same patient will be pooled and used directly for acid-fast bacilli smear, Xpert MTB/XDR and MGIT and LJ culture.

Appropriate laboratory staff at each site reference laboratory are responsible for receiving the samples, storing the samples and conducting all testing in line with BSL3 requirements. All leftover samples must be stored until study conclusion and completion of all analyses, in case any additional or repeat testing is requested by the sponsor.

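### Frozen sputa may top up the consecutive series, but the documents disagree on whether they are analysed, and no planned analysis separates them from fresh samples

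*Protocol*

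**What the plan says.** Protocol 5.3.1, part of the section on minimising error and bias, relies on consecutive enrolment: "A consecutive series of Xpert MTB/RIF MTB-positive patients (n=284) will be enrolled in this study", then a consecutive series of 316 RIF-resistant patients.

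Protocol 6.1.1 opens a second source, to shorten timelines: "existing, well-characterized frozen TB clinical (sputum) samples collected during the course of routine clinical care". The condition is "These samples will only be used if recruitment or enrolment is slow at one or more sites", and the decision point is "At the 4-week study time point, recruitment rates will be assessed to determine whether this use of additional samples will be necessary". The section defines no slow rate, cap, selection rule or storage limit. It does not say how consent applies to these samples or which enrolment stage they would count towards.

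Other places leave no room for such samples:

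- Protocol section 7: "Clinical (sputum) samples from enrolled patients will be used in this study".
- Protocol 5.2.2 restricts testing with the index assay to samples of enrolled participants.
- SAP 3.2 defines the intention-to-test set as successfully enrolled subjects. The per-protocol set, used for outcomes 1.1 to 1.3, is a subset of it.

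On the analysis side, Protocol 9.2 lets all TB samples with both an Xpert MTB/XDR and a composite reference result contribute to accuracy. The exclusion lists in Protocol 9.2.1 and SAP 3.2 do not mention frozen samples. SAP 4.3 splits specimens into sputum and culture only. SAP section 7 adds: "No additional subgroup analyses will be performed".

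**The concern.** Consecutive enrolment is the plan's stated protection against selection bias. A sample taken from a freezer because it is already well characterised does not enter by that route, and storage may change how it performs. Either effect could alter sensitivity, specificity or the non-determinate rate, all of which belong to the primary objectives (1.1 to 1.4). If fresh and frozen samples are reported as one group, a reader cannot tell whether the result describes the consecutive series or the mixture. The confidence interval does not reflect this error.

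Two further rules could hide a storage effect. Frozen sputa that are smear-positive but fail to grow leave the primary analysis (Protocol 9.2.1). Where the sputum and isolate Xpert results disagree, the isolate result is used (Protocol 9.2), so a direct-test failure caused by storage may not show in the primary accuracy figure.

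**Working it through.** **1. The plan's own figures.** Protocol Appendix 4 allows 21% attrition: 360 × 0.79 = 284.4 and 400 × 0.79 = 316, so 600 analysable samples. Table 2 (Protocol 9.1, SAP section 10) reproduces within rounding with the continuity-corrected Wilson interval at 90% sensitivity:

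| Drug | n resistant | 95% CI |
|---|---|---|
| INH | 395 | 86.5-92.7% |
| FQ | 93 | 81.6-95.0% |
| KAN | 71 | 80.0-95.5% |
| AMK/CAP | 34 | 73.7-97.1% |

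The sample size is not in error. The question is where the samples come from.

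**2. Are frozen samples in the analysis?** Two readings are possible.

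- *Protocol 9.2 governs.* A frozen sputum with both results enters the primary analysis, no exclusion removes it, and no planned split identifies it.
- *SAP 3.2 governs.* A frozen sputum from someone not enrolled is outside both the intention-to-test and per-protocol sets. It then cannot count towards the 600, and the allowance in 6.1.1 fails its purpose. Protocol 5.2.2 would bar testing it at all.

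Nothing in the documents chooses between these readings.

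**3. Possible size if pooled.** Let f be the frozen share of the resistant samples for a drug, and d the sensitivity in frozen minus that in fresh samples. Then

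pooled sensitivity = fresh sensitivity + f × d.

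The documents give neither f nor d, so both are assumed. Fresh sensitivity is set at the planning value of 90%.

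| f | d = -10 | d = -5 | d = +5 | d = +8 |
|---|---|---|---|---|
| 10% | 89.0% | 89.5% | 90.5% | 90.8% |
| 25% | 87.5% | 88.75% | 91.25% | 92.0% |
| 50% | 85.0% | 87.5% | 92.5% | 94.0% |

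The shift runs from -5 points (0.50 × -10) to +4 points (0.50 × 8). For comparison, the planned half-width is about 3 points for INH (6.2/2) and about 12 for AMK/CAP (23.4/2). The same formula applies to the non-determinate rate, with f as the frozen share of all samples tested. The documents give no basis for d there either.

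**4. Precision of a prospective-only estimate.** This uses the same interval method at 90%, with frozen samples removed:

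| Frozen share | INH | FQ | KAN | AMK/CAP |
|---|---|---|---|---|
| 10% | n=355, 86-93% | n=84, 81-95% | n=64, 79-96% | n=31, 73-97% |
| 25% | n=296, 86-93% | n=70, 80-96% | n=53, 78-96% | n=26, 71-98% |
| 50% | n=197, 85-94% | n=47, 77-96% | n=35, 74-97% | n=17, 64-99% |

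**The case against.** A reader might infer that banked samples would be picked for known resistance, would be cleaner than fresh sputa, and would therefore raise accuracy. The top right-hand direction of the table in step 3 (94% against 90%, if half the AMK-resistant samples were frozen with sensitivity 98%) would then look like a forecast. The documents do not support that. Well-characterised does not mean chosen by resistance, and the stated purpose is to save time. No passage says that frozen sputa perform better, and freezing could equally lower performance. Nor does prior culture growth separate the two sources for accuracy: fresh samples also need a positive culture, because DST and NGS are done on the isolate (Protocol 6.1.2 and 7.1).

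Other parts of the defence also stand. Frozen samples are a contingency and may never be used. The SAP nowhere states that sources are pooled, and read strictly its analysis sets leave frozen samples out. Protocol 10.4 already offers another answer to a slow site, which is to continue at the others. The case report form is not among the documents, so a source field may exist. Estimates by site (SAP 4.3) might show a difference if one site alone used frozen samples, though it would be confounded with site. Using the isolate result for discordant pairs also limits how far storage can move the primary accuracy figure.

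It might also be argued that frozen use is likely, since 400 RIF-resistant patients at Appendix 4's 23% imply about 1,740 MTB-positive patients (400/0.23). That is insecure. Protocol 4.1 admits patients already diagnosed with MDR-TB, and the sites routinely handle many drug-resistant samples, so Stage 2 need not draw on unselected MTB-positive patients.

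What the defence does not answer is the contradiction over status, the missing selection rule and the absence of any planned analysis by source.

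**Conclusion.** The point holds as a conditional risk together with a definite inconsistency. The inconsistency needs no assumption: Protocol 6.1.1 permits samples that Protocol 5.2.2, 5.3.1 and 7 and SAP 3.2 do not provide for, while Protocol 9.2 would admit them. The bias arises only if frozen samples are used and pooled. Its direction is unknown and the documents do not fix its size. The range of about -5 to +4 points rests wholly on the assumed shares and differences. At its extremes it exceeds the planned INH half-width but lies well inside that for AMK/CAP. The unknown direction is itself a reason for separate reporting, since a pooled figure could not be corrected afterwards. This is an inexpensive improvement that should be made; it does not show the planned estimates to be wrong.

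**What to change.** 1. Reconcile Protocol 6.1.1 with Protocol 5.2.2, 5.3.1 and 7 and SAP 3.2. State whether frozen samples enter the analysis sets and how the consent criterion applies to them.
2. Record the source of each sample (prospective or frozen) on the case report form, if it is not already there.
3. In SAP 4.2, provide that if frozen samples are used, the prospective consecutive series gives the primary estimate, or is at least reported beside the combined one, for both accuracy and non-determinate rates. Adjust SAP section 7 to match.
4. In Protocol 6.1.1, require frozen samples to be taken consecutively by collection date, using only the Xpert MTB/RIF or Ultra result and the other eligibility criteria. Known DST, sequencing, LPA or Xpert MTB/XDR results should play no part. A bar on using any Xpert result would not work, because eligibility, and entry to Stage 2, depend on the Xpert MTB/RIF or Ultra result.

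The cost is at most one data field, one extra column in the accuracy tables and some wording. If no frozen samples are used, nothing is lost. If they are, the prospective-only interval is wider, as in step 4 of the working; the worst case there is AMK/CAP, at about 64-99% against the planned 74-97%.
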